 - o No visible damage to either the PCIOL or the IOPCL
 - o Uniform leaflet coverage of all IOPCL haptic tabs
- Long-term adherence and positional stability
 - Minimal Change in uniformity of the gap between 1-2 months and 4-6-months as determined by UBM measurements. Minimal change is defined as +/- 10 microns between visits is established and maintained using UBM imaging
- Characterization and incidence of cumulative and persistent intraoperative and post-operative adverse events.

Stopping Rules

The Sponsor or the clinical investigator can suggest suspension of the clinical trial at any time if they are in receipt of information that leads them to believe that continuing the study jeopardizes the health and welfare of the clinical trial participants. Suspension of the study will be considered if two or more consecutive severe ocular injuries occur at any one clinical site that are related to the surgical procedure and/or IOPCL device. A severe ocular injury results in a permanent impairment of a vision or permanent damage to an eye.

Examples:

- Uveitis-Glaucoma-Hyphema (UGH) Syndrome. Intraocular chafing from the IOL/PCIOL implant leading to a spectrum of iris transillumination defects and pigmentary dispersion to microhyphemas with elevated intraocular pressure.
- Posterior capsule rupture with IOL/PCIOL dislocation resulting in a posterior vitrectomy during the surgical procedure

Primary Effectiveness Endpoint

Proportion of eyes ($\geq 50\%$) able to achieve a stable target refraction, (manifest or autorefraction) within 0.5 D of the intended target. Stability is achieved when there is no change (± 0.50 D) within two consecutive postoperative visits at 1 month or later visits.

04-08-2021 5

3. Subject Population

A maximum of 10 pseudophakic eyes will be implanted unilaterally with the AccuraSee IOPCL.

3.1. Inclusion Criteria:

- 1. Subjects who have already had cataract surgery with a Bausch and Lomb monofocal intraocular lens model LI61A0 (with lens power from 18.0 diopters (D) to 23.0 D) or model LI61SE (with a lens power from18.0 D to 22.5 D), as clearly evidenced by photographic documentation with one of the following: (1) patient medical record, (2) clinic chart with labeling attached, (3) surgical record with labeling attached, or (4) patient identification card with make, model, power, and serial number.
- 2. Able to comprehend and sign a statement of informed consent.

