CAUTION: It is important to place the IOPCL in the center of the cartridge chamber so that the haptics are well away from the edges of the flaps when they are folded closed. Otherwise the haptics may get caught between the flaps and become torn when the plunger is pressed to advance the IOPCL in the injector. It is also suggested that additional ProVisc be placed at the posterior entrance to the cartridge so as to provide a buffer between the plunger and the folded IOPCL. It is also suggested while closing the cartridge to press down on the center of the optic to assure the haptics remain free of the cartridge flap. Carefully push the plunger forward to ensure that the silicone tip correctly enters the loading chamber, while making sure not to capture one of the haptics between the plunger and the cartridge wall. Continue to push the tip until the inner spring begins to compress. Pull the plunger back a few millimeters and then push it forward again. This step ensures that the lens is correctly grasped.

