Inject the IOPCL with the leading haptic forward denoted by the "R" inversion mark into the anterior chamber of the eye, thru the previously placed 2.5mm cornea incision. Using angled intraocular manipulating hooks such as Sinskey or collar button, rotate the IOPCL to line up the haptics with the previously placed channels and guide the haptics into each of the 3 channels. Once distal haptics are firmly seated, grasp leading haptic with surgical tool of choice through either the 1.5 mm paracentesis incision or initial 2.5 mm incision and advance the leading haptic under the anterior leaflet into awaiting 1.5 mm tunnel. If needed introduce a second instrument through paracentesis incision to aid in lifting edge of capsule to ease the advancement of the leading haptic into created tunnel. After placing each haptic, confirm that it is beneath the anterior flap, properly seated and has captured the edge of the existing PCIOL. Ensure that there is no interference between the haptics of the pre-existing PCIOL and the IOPCL. The optic of the IOPCL should be flat and well centered to the existing PCIOL. Irrigate and aspirate all residual ProVisc and any displaced material from the anterior chamber. Once all three haptics are resting unrestricted, using light rocking motion, manipulate the IOL to assure the tri-haptic system has a uniform grasp to the edge of the underlying IOL. Finally, confirm that the IOPCL remains well centered with the haptics well secured under the anterior leaflet capsule. Hydrate and close the incision per your normal anterior chamber procedures.

REMOVING CELLULAR MATTER (OPACIFICATION) BETWEEN THE IOL AND IOPCL

Using an irrigating cannula and BSS loosen the cortical/cellular material between the two lenses from the periphery, followed by removal with a coaxial/aspiration (I/A handpiece). Alternatively utilize a bi-manual I/A system with separate irrigation and aspiration handpieces. These small handpieces can be introduced through two 1.0 mm paracentesis incisions and can easily fit between the two lenses delivering irrigation from one side and aspiration from the opposite side to remove any cortical or interlenticular cellular material place a small amount of ProVisc® within the angle of the anterior chamber to stabilize the chamber while allowing for free flow of BSS fluid. Use a straight 27 gauge

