- ➤ Malpositioned/Misaligned Optics (IOPCL not centered over PCIOL)
 - o Early[1]
 - o Late[2]
- Unseated IOPCL haptic tabs (One or more haptic tabs not securely attached to the PCIOL)

- > Post Nd:YAG Posterior capsulotomy event
- > Lens Optical Performance
- Mechanical Failure
- Vitreous Aspiration for Pupillary Block
- Corneal Stroma Edema
 - Corneal Edema with BCDVA of 20/40 or worse at Form 3 (1-2M post-op) or later
- > Iritis present at 1-month or later
- Macular Edema present at 1-month or later
- > Raised IOP requiring treatment
 - Raised IOP, greater than 10 mmHg above baseline and to a minimum of 25 mmHg.
- ➤ Iris Chafing
- > Iris Trauma and/or Damage
- > Iris Transillumination Defects
- > Pigment Dispersion
- > Pseudophacodonesis or Evidence of Zonular Trauma/dehiscence
- > Inter-device opacification or fibrosis between the PCIOL and IOPCL
- > Other

```
[1]Early – prior to Form 4 visit window (i.e., < 120 days)
[2]Late – At 120 days or later
```

Note: Secondary Surgical Intervention(s) (SSI) may be necessary to resolve any of the adverse events identified above. If an SSI is conducted in the trial, the details of the SSI and corresponding reason for SSI will be documented on the SSI CRF.

Examples of Secondary Surgical Interventions

- ➤ Irrigation of IOPCL/IOL Interface
- > Exchange
- ➤ Reposition of the same Implantable Pseudophakic Contact Lens
- ➤ Removal

13. Adverse Experience and Complication Reporting

Throughout the course of the proposed study, all efforts will be made to remain alert to possible adverse experiences or untoward findings. If adverse experiences occur, the first concern will be the safety and welfare of the subject and appropriate medical intervention will be made. Any adverse experiences observed by the investigator or reported by the subjects, whether or not ascribed to the investigational procedure or device, will be recorded on the subjects' adverse event case report form. A new adverse event case report form is used for each adverse event or adverse event related visit.

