3.2 Safety Endpoints

Preservation of Best Corrected Distance Visual Acuity (BCDVA)

The preservation of BCDVA is defined as proportion of eyes (< 5%) that lose two or more lines of BCDVA from baseline.

• Successful Delivery of the IOPCL as determined at 7-14 days post-operative

The successful delivery of the IOPCL is defined as no capsular tear, visualize centration between the IOL and IOPCL, no visible damage to either the IOL or IOPCL, and uniform leaflet coverage of all IOPCL haptic tabs.

• Long-term Adherence and Positional Stability

The long-term adherence and positional stability is defined as minimal change (i.e. \pm 10 microns) between 1-2 months and 4-6- months as determined by UBM measurements. The open central spacing between the IOL and IOPCL is established and maintained using UBM imaging.

Adverse Events

The Adverse Events is defined as characterization and incidence of cumulative and persistent intraoperative and post-operative adverse events.

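### Successful delivery requires the haptic tabs to be covered by the capsule leaflet but not locked to the PCIOL edge, so an eye with an unseated tab can still count as a success

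*SAP*

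**What the plan says.** SAP 3.2 introduces the endpoint as "Successful Delivery of the IOPCL as determined at 7-14 days post-operative". It then gives the definition: "The successful delivery of the IOPCL is defined as no capsular tear, visualize centration between the IOL and IOPCL, no visible damage", with the closing items reading in full "no visible damage to either the IOL or IOPCL, and uniform leaflet coverage of all IOPCL haptic tabs". Protocol section 2, Safety Endpoints, lists the same four items, and its only item about the tabs is "Uniform leaflet coverage of all IOPCL haptic tabs". SAP 7.5.2 reports the number and percent of eyes that succeed, on observed data. It sets no threshold, test or explicit denominator.

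Other sections treat attachment to the underlying lens as a separate matter:

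- Protocol sections 1 and 9 describe a pawl under each haptic that locks onto the optic edge of the implanted lens.
- Protocol section 9, Insertion of the IOPCL, tells the surgeon to check each haptic and "confirm that it is beneath the anterior flap, properly seated and has captured the edge of the existing PCIOL".
- Protocol section 12 lists unseated haptic tabs as a postoperative adverse event, explained as "One or more haptic tabs not securely attached to the PCIOL".

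**The concern.** The primary objective in both documents is that the lens adheres to the implanted lens without rotation or slippage. Delivery is the endpoint read earliest after surgery, so it is the natural place to establish that attachment was achieved at the outset. As written, it checks that the capsule covers the tabs and does not check that the tabs hold the optic.

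At stake is what the reported percentage means. A reader of the feasibility report would take successful delivery to mean that the device was placed as designed. Under the present rule the percentage can include eyes in which the attachment mechanism is not engaged.

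**Working it through.** The documents give no target rate, power or derived sample size for this endpoint, so there is no stated figure to reproduce. The check is a comparison of passages, followed by simple arithmetic for scale.

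**Step 1. Compare the surgical check with the endpoint.**

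| Feature of correct placement | Surgical check (Protocol 9) | Delivery endpoint (Protocol 2, SAP 3.2) | Adverse event if absent (Protocol 12) |
|---|---|---|---|
| Haptic under the leaflet | yes | yes, as leaflet coverage | not listed as such |
| Haptic seated, edge captured | yes | no | yes, unseated tab |
| Optic centred | yes | yes | yes, malpositioned optic |

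The section 9 instructions separate capture from cover twice. They do so once for each haptic, and again at the end, when the surgeon rocks the lens to test the grip on the optic edge and then confirms that the haptics are secure under the leaflet.

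**Step 2. Apply the four items to an eye with one unseated tab.** No item tests the lock directly. The eye passes if there is no capsular tear, the lenses are centred, neither is visibly damaged and the tab is still covered. It fails only if the unseated tab also disturbs centration or coverage.

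**Step 3. See whether another endpoint closes the gap.** Long-term adherence (SAP 3.2 and 7.5.3) counts eyes whose UBM measurement changes by no more than 10 microns between 1-2 and 4-6 months. It measures change from the first of those visits. A tab that never locked, with a gap that stays constant, can satisfy it too.

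**Step 4. Size.** One reclassified eye among N evaluable eyes moves the rate by 100/N points. The maximum is 10 eyes (SAP 6.2).

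- N = 10: 100/10 = 10 points. The rate goes from 10/10 = 100% (exact 95% interval 69.2 to 100) to 9/10 = 90% (55.5 to 99.7).
- N = 8, as an illustration: 100/8 = 12.5 points. The rate goes from 8/8 = 100% (63.1 to 100) to 7/8 = 87.5% (47.3 to 99.7).

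The documents give no probability of an unseated tab, so any expected overstatement would only restate an assumed rate.

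**The case against.** The strongest reply is that the failure is reported elsewhere. Adverse events and delivery are separate safety endpoints in SAP 3.2, and SAP 7.5.4 tabulates each event by visit and cumulatively. The count of unseated tabs at 7-14 days would therefore appear in the same report as the delivery rate, and with at most 10 eyes a careful reader could put the two together. This stands. It also disposes of one tempting inference, that the endpoint contradicts the adverse-event list. An eye can meet one safety endpoint and still have an event under another. The defect is only that the two are not linked.

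A second reply also stands. The protocol says that the pawl helps centre the lens, so an unseated tab may fail the centration or coverage item anyway. Misclassification is possible, not automatic.

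Third, a reader might infer that only the lens finally in the eye is judged, so that a first lens torn in the injector and replaced leaves a success on record. Protocol section 9 does warn about loading: "Otherwise the haptics may get caught between the flaps and become torn when the plunger is pressed". But no passage says that only the final lens counts. The no-damage item can be read as covering any lens used, or only the one seen at 7-14 days. Replacement by another lens is described only for debris between the lenses. The documents are silent on this case, and silence is not a rule that such an eye succeeds. Making first-lens success a condition would change the outcome to first-attempt delivery, which is a preference and not a correction.

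Finally, the endpoint is descriptive, so no test or decision rule is affected. That limits the consequence but leaves the meaning of the percentage unclear.

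**Conclusion.** The point holds in this form: both documents define successful delivery without edge capture, although the protocol makes capture the attachment mechanism, checks it separately at surgery and lists its absence as an adverse event. A centred, covered, undamaged eye with no capsular tear and an unseated tab is a success under the rule as written. Each such eye raises the reported rate by 10 points with 10 evaluable eyes, and by more with fewer.

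This rests on reading the four items as the complete definition, which is how both documents present them. It does not depend on any assumed frequency of unseated tabs. The consequence is a possible misclassification in a descriptive percentage.

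**What to change.** In Protocol section 2 and SAP 3.2 and 7.5.2:

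1. State that successful delivery also requires edge capture of all three tabs confirmed during surgery, using the check already in Protocol section 9, and no unseated-haptic-tab event up to and including the 7-14 day visit.
2. Report n/N over all eyes in which implantation was attempted, the population in SAP 5, for the composite and for each component.
3. Report the number of lenses used per eye descriptively from the device accountability records (Protocol 15.2), without making first-lens success a condition.

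The cost is a few sentences in each document and a success rate that may be lower. No new examination is needed. UBM is not scheduled at 7-14 days (Protocol 11), so the definition should rest on the surgical confirmation and the adverse-event record. The case report forms are not among the documents reviewed. If the operative form has no field for edge capture, one should be added; for eyes already operated on, the surgical videos required by Protocol section 9 are a possible source.

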3.3 Other Clinical Outcomes

- Auto-refraction
- Visual acuity parameters (BCDVA)
- Slit lamp examination
- Applanation intraocular pressure (IOP) using Goldmann
- Dilated fundus examination
- Visual symptoms (QoV)

4 STUDY DESIGN

This will be a three (3) center US clinical trial, in which a maximum of 10 subjects will be implanted unilaterally with the AccuraSee IOPCL and followed for 12 months.

The subjects who might be eligible are potentially interested in participating and have provided their informed consent will be examined preoperatively to obtain a medical history and to establish a baseline for their ocular condition. Qualified subjects who provide written consent will be enrolled into the study.

Subjects will undergo IOPCL implantation. Postoperatively, subjects will undergo a complete ophthalmic evaluation at regularly scheduled intervals in accordance with study protocol.

An Investigational Device Exemption (IDE) application will be submitted on clinical outcomes when all enrolled eyes have a chance of reaching the 4-6-month post-operative visit (Postop Form 4).

This study is being conducted in accordance with 21CFR, Parts 50, 54, 56 and 812.42 (U.S.C 282(j)). ISO 14155 Clinical investigation of Medical Devices for Human Subjects, ISO 11979-7, and the ethical principles laid down in the Declaration of Helsinki.

5 ANALYSIS POPULATIONS

The analyses will include the data of all study eyes where implantation of IOPCL was attempted and/or successful.

6 STATISTICAL CONSIDERATIONS

6.1 General Considerations

Descriptive statistics (mean, median, standard deviation, minimum, and maximum) will be used to summarize continuous variables. Frequencies and percentages will be used to summarize categorical variables.

Any analysis not described in this plan will be considered exploratory, and will be documented in the clinical study report (CSR) as a post hoc analysis or a change to the planned analysis.

6.2 Sample Size

Sample size is limited to maximum of 10 subjects (eyes) for this Early Feasibility Study (EFS).

6.3 Randomization and Masking

This study will not be randomized or masked.

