To determine if the intraocular pseudophakic contact lens (IOPCL), referred to as the AccuraSee, provides refractive correction using a plus powered lens in subjects with ocular pathology previously implanted with a Bausch and Lomb LI61AO or LI61SE monofocal posterior chamber intraocular lens (PCIOL) and to confirm its positional stability and adherence relative to the PCIOL.

Study Design:

This will be a 12-month three center study, in which a maximum of 10 pseudophakic subjects will be enrolled.

This study is being conducted in accordance with 21 CFR Parts 50, 54, 56 and 812.42 (U.S.C 282(j)). ISO 14155 Clinical investigation of Medical Devices for Human Subjects, ISO 11979-7, and the ethical principles laid down in the Declaration of Helsinki.

1. Introduction and Rationale

The AccuraSee (intraocular pseudophakic contact lens) consists of a 4.5 mm diameter concave-convex optic with three opposing haptic straps, or tabs. The haptic straps are designed to enter and rest within three channels created under the anterior leaflet of the capsular bag. Each channel is created with a Cady-Soiseth Capsule Separator spatula. Each haptic strap or tab has a small pawl, or ridge on the bottom that is used to catch and lock on to the IOL optic edge. This pawl aids in both centering the AccuraSee on the IOL optic as well as allowing the haptic strap to stay securely seated while contained under the surface tension of the anterior leaflet of the capsular bag. The lens is designed to fine-tune the residual refractive error of the longstanding pseudophakic eye. The lens design, position and surgical approach are intended to lessen the complication rate and overall invasive nature of today's available secondary lens implantation technologies.

2. Study Objective

The primary objective of this study is to determine the stability of the AccuraSee to successfully adhere to a pseudophakic intraocular lens without rotation or slippage.

The secondary objective of this study is to determine if the AccuraSee can successfully change refraction up to +3.0 diopters (D) in subjects previously implanted with an Bausch and Lomb LI61AO and LI61SE monofocal intraocular lens.

Safety Endpoints

- Preservation of BCDVA Proportion of eyes (< 5%) that lose two or more lines of BCDVA from baseline.
- Successful delivery of the IOPCL as determined at 7-14 days post-operative
 - o No capsular tear
 - o Visualize centration between the PCIOL and IOPCL

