10.2 Unscheduled / Interim Visits

Additional visits may be scheduled as deemed necessary by the investigator, to ensure the safety and well-being of the subject.

11. Clinical Assessments

All parameters will be recorded for both eyes at baseline (pre-operative). Measurements will be recorded for the study eye at postoperative and post-removal visits. See Appendix 2A schedule of visits (pre and post-operative visits) and Appendix 2B (post-removal visits). See Appendix 3 for clinical assessment instructions

- Inclusion/exclusion criteria: Preoperative
- Medical history: Preoperative
- Demographics: Preoperative
- Patient Informed Consent: Preoperative
- Measurements: Make and Model # of Equipment Preoperative
- Axial Length & Keratometry Preoperative
- Capsulorhexis Size at the time of IOL surgery: Preoperative
- Position of IOL Haptics and IOPCL Incision Location: Preoperative
- Mesopic and Photopic Pupil size measured by Pupilometer: Preoperative

- Predicted Post-Op Refraction: Preoperative
- Pseudophakic IOL power with make and model number: Preoperative
- Spatial Visualization between the PCIOL and IOPCL Using UBM: 30-60 days, 120-180 days, 330-420 days, Interim.
- Recording of the IOPCL Surgical Procedure: Operative
- UCDVA: Uncorrected Distance Visual Acuity Preoperative, 7-14 days, 30-60 days, 120-180 days, 330-420 days. Interim
 - Post-removal, 7-14 days, 30-60 days, 120-180 days, 330-420 days. Interim
- UCIVA: Uncorrected Intermediate Visual Acuity Preoperative, 7-14 days, 30-60 days, 120-180 days, 330-420 days. Interim
 - Post-removal, 7-14 days, 30-60 days, 120-180 days, 330-420 days. Interim
- UCNVA: Uncorrected Near Visual Acuity Preoperative, , 7-14 days, 30-60 days, 120-180 days, 330-420 days, Interim.
 - Post-removal, 7-14 days, 30-60 days, 120-180 days, 330-420 days. Interim
- BCDVA: Best Corrected Distance Visual Acuity Preoperative, 7-14 days, 30-60 days, 120-18 days, 330-420 days, Interim
 - Post-removal, 7-14 days, 30-60 days, 120-180 days, 330-420 days, Interim
- Manifest Refraction: Preoperative, 7-14 days, 30-60 days, 120-180 days, 330-420 days, Interim
 - Post-removal, 7-14 days, 30-60 days, 120-180 days, 330-420 days, Interim
- Auto-refraction: Preoperative, 7-14 days, 30-60 days, 120-180 days, 330-420 days. Interim
 - Post-removal, 7-14 days, 30-60 days, 120-180 days, 330-420 days, Interim.
- Slit Lamp Examination: Preoperative, 1-2 days, 7-14 days, 30-60 days, 120-180 days, 330-420 days. Interim

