- IRB approvals for the study protocol, all amendments and informed consent form(s)
- IRB annual study review,

04-08-2021 20

- Subject's signed informed consent form,
- Correspondence from and to the Sponsor, and
- Any other documents relevant to the conduct of the study.

18. Study Monitoring

OnPoint Vision Inc. personnel (or designees) will monitor all clinical studies in a manner consistent with good clinical practices (GCPs) and all applicable health authority regulations, and in accordance the study monitoring plan. Study monitoring will involve the following elements.

- 1. OnPoint Vision Inc. personnel (or designee) will meet with the investigator(s) prior to the initiation of the study in order to review the adequacy of the subject population, facilities, and equipment with respect to the needs of the study, and to familiarize the investigator with the study protocol.
- 2. OnPoint Vision Inc. personnel (or designee) will meet with the investigator(s) at the time study subjects begin to be enrolled in order to ensure that subjects are being properly selected and that study data are being correctly recorded.
- 3. OnPoint Vision Inc. personnel (or designee) may remotely review and audit or visit the clinical site at any time during the study to review the case report forms and verify data against medical records.
- 4. Interim monitoring visits and telephone consultation will occur as necessary during the course of the study to ensure the proper progress and documentation of the study findings.

Sponsor field staff under the supervision of the investigator will periodically visit investigational sites to ensure that study procedures (e.g., refractions, visual acuity measurements) are performed consistently and in compliance with protocol-specified techniques, and in doing so may come in direct contact with study subjects. The rights and well-being of subjects are protected, and the study is being conducted in accordance with 21CFR, Parts 50, 54, 56 and 812.42 (U.S.C 282(j)). ISO 14155 (2011) Clinical investigation of Medical Devices for Human Subjects, ISO 11979-7, and applicable local regulations and the ethical principles laid down in the Declaration of Helsinki (see Appendix 4).

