7.5.3 Long-term Adherence and Positional Stability

The analysis of this clinical outcome will be based on the observed data of AccuraSee IOPCL. The number and percent of eyes with minimal change (i.e. \pm 10 microns) between 1-2 months and 4-6- months established and maintained central spacing between the IOPCL and IOL will be reported.

Long-term adherence and positional stability will also be stratified by the surgical technique (e.g., discrete narrow channels or wider sweeping channels).

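### The plan states no safeguard for reading the UBM images, so a reader who knows the first value could bias the ±10 micron agreement endpoint towards stable

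*SAP*

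**What the plan says.** Protocol section 2 sets the primary objective: to "determine the stability of the AccuraSee to successfully adhere to a pseudophakic intraocular lens without rotation or slippage". The measure that serves it is long-term adherence and positional stability, which both documents list under safety endpoints. The protocol states "Minimal change is defined as +/- 10 microns between visits", and SAP 3.2 places the comparison "between 1-2 months and 4-6- months as determined by UBM measurements". SAP 7.5.3 reports "The number and percent of eyes with minimal change", with no test and no success threshold, and stratifies the result by surgical technique.

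On masking, SAP 6.3 says only "This study will not be randomized or masked". Protocol section 11 schedules "Spatial Visualization between the PCIOL and IOPCL Using UBM: 30-60 days, 120-180 days, 330-420 days, Interim" and refers to Appendix 3 for assessment instructions; the text of that appendix is not in the supplied documents. The supplied text names no UBM reader, reading order or rule on access to earlier values.

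For refraction, the primary effectiveness endpoint requires a result within 0.5 D of target and a change of no more than ±0.50 D between consecutive visits. The predicted postoperative refraction is recorded before surgery (Protocol section 11). SAP 7.4.2 repeats the analysis with autorefraction because poor acuity can make manifest refraction unreliable.

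**The concern.** An agreement endpoint is exposed to one particular reading error. If the person measuring the second image knows the first value and is drawn towards it, the difference shrinks and more eyes fall inside the margin. If repeat readings were made with the same knowledge, averaging them would not remove that pull.

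Three features raise the stakes. With at most 10 eyes (SAP 6.2), one reclassified eye moves the result by at least 1/10, or 10 percentage points. The interim analysis falls at 4-6 months (SAP 6.8), and SAP 4 ties an IDE application to outcomes at that visit. The comparison by surgical technique could also be affected if the reader knows which technique was used.

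Manifest refraction is exposed in the same way, because success means agreement with a predicted value and with the previous visit. Eligible eyes see 20/80 or worse (Protocol 3.1), which leaves room for expectation in a subjective measurement.

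**Working it through.** **No plan figure to reproduce.** Ten eyes is a cap and not a calculated sample size, and the endpoint is descriptive. The documents give no UBM repeatability figure. The calculations below show direction and sensitivity only.

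**Input from the documents:** margin 10 microns (Protocol section 2; SAP 3.2 and 7.5.3).

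**Assumptions:** share w of the difference lost when the reader is drawn to the first value (0, 0.25, 0.50); reading error SD σ per visit (5, 10, 20 microns); true shift δ (0 or 20 microns).

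**Model A, fixed true shift with reading error.** Observed difference = (1−w)(δ + e2 − e1), with each e ~ N(0, σ²). Its mean is (1−w)δ and its SD is (1−w)σ√2. Then

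P(stable) = Φ[(10 − (1−w)δ) / ((1−w)σ√2)] − Φ[(−10 − (1−w)δ) / ((1−w)σ√2)].

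Example: δ = 20, σ = 10, w = 0.50 gives mean 10 and SD 7.07, so P = Φ(0) − Φ(−2.83) = 0.498.

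| δ | σ | w = 0 | w = 0.25 | w = 0.50 |
|---|---|---|---|---|
| 0 | 5 | 0.843 | 0.941 | 0.995 |
| 0 | 10 | 0.520 | 0.654 | 0.843 |
| 0 | 20 | 0.276 | 0.363 | 0.520 |
| 20 | 5 | 0.079 | 0.173 | 0.500 |
| 20 | 10 | 0.223 | 0.309 | 0.498 |
| 20 | 20 | 0.217 | 0.288 | 0.421 |

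In ten eyes with no true shift and σ = 10, the expected number called stable rises from 5.2 to 8.4 at w = 0.50.

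**Model B, true changes varying between eyes, no reading error.** P = 2Φ(10 / ((1−w)SD)) − 1.

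| SD of true change | w = 0 | w = 0.25 | w = 0.50 |
|---|---|---|---|
| 10 | 68% | 82% | 95% |
| 15 | 49.5% | 63% | 82% |
| 20 | 38% | 49.5% | 68% |

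**Both sources together.** With true SD 10 and σ = 10, the SD of the difference is √(100 + 2×100) = 17.3 microns. At w = 0, P = 2Φ(10/17.3) − 1 = 44%; at w = 0.25 it is 56%. Both lie below the error-free 68%. Random reading error lowers the stable count while a pull raises it, so Model B does not predict what the study would report.

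**Sampling uncertainty for scale.** The exact 95% interval is 44% to 97% for 8 of 10 stable, and 69% to 100% for 10 of 10.

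**The case against.** The strongest reply is that the documents do not describe the reading at all. One study-level sentence in a single-arm SAP is a statement about treatment; it does not forbid reading images without knowledge of the visit. Appendix 3 may hold reader instructions. This stands in part. A reader of SAP 6.3 might infer that whoever measures the second image can see the first value, and that results are therefore pulled towards stable. Neither follows: the supplied text is silent on who reads and what they see. What remains is that the plan permits such reading and states no safeguard.

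Second, the measure is labelled a safety endpoint, is reported descriptively in at most ten eyes, and a gap measurement does not capture rotation. All true. It is still the only quantified between-visit stability measure serving the primary objective.

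Third, the pull is assumed, and a reader watching for slippage could err the other way. That is correct. It limits what can be said about size and direction, but withholding earlier values guards against either error.

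Fourth, for refraction, the autorefraction repeat in SAP 7.4.2 already gives partial protection. It does; it does not protect the manifest refraction itself.

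A reader might also infer sponsor influence from the statement in Protocol section 18 that field staff "may come in direct contact with study subjects". The text does not support this: those visits are under the investigator's supervision and check that procedures are consistent and compliant. Nothing says that these staff measure or influence refractions.

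**Conclusion.** The concern holds as an unaddressed risk. The study is declared unmasked, the supplied text gives no safeguard for UBM reading, and the endpoint rewards agreement between two visits, so a reader who knows the first value can bias the count towards stable. Whether this would happen, and by how much, cannot be derived from the documents. Under Model A, a 50% pull raises the chance that an eye with a true 20 micron shift is called stable from 8-22% to 42-50%. These figures depend entirely on the assumed pull, shift and reading error; the Model B figures also leave reading error out. The change is worth making because it is inexpensive and the endpoint feeds the 4-6 month analysis. The gap does not invalidate the study.

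**What to change.** In SAP 6.3, SAP 7.5.3 and Protocol section 11, state that treatment is unmasked, but that endpoint UBM measurements are made by existing study readers on saved images with subject, date and visit removed, in random order and without access to earlier values.

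Read the Form 3 and Form 4 images once, before the 4-6 month analysis, and lock those values as the endpoint. A single locked reading avoids two competing sets of values for the same comparison. Read the Form 5 images later in the same way, as supportive data. That later batch holds only one visit, so withholding earlier values is the main protection there.

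For refraction, take autorefraction first and do not show the examiner the predicted refraction or the previous visit's value.

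If Appendix 3 already specifies masked reading, reconcile it with SAP 6.3.

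Cost: at most 2 × 10 = 20 images for the endpoint and 10 more from Form 5, with no added subject, visit or procedure. Images must be exported, and endpoint readings become available later than readings made at the visit. That images are saved and that existing readers can do this are assumptions, since the supplied text describes neither. Masking does not reduce random reading error.
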